5.5.1.2. Endoscopic

Endoscopic Remission

The definition of endoscopic remission is SES-CD ≤ 4 and at least a 2-point reduction from baseline and no subscore greater than 1 in any individual component.

NOTE: All 3 of the following conditions must be met to be in endoscopic remission:

- Total SES-CD score is ≤ 4
- None of the 20 individual cells making up the Total SES-CD can be greater than 1
- Change from Baseline in Total SES-CD score is at least a 2-point decrease

Endoscopic Remission (Alternative Definition)

The *alternative* definition of endoscopic remission is an SES-CD Score ≤ 2 .

Endoscopic Healing

Endoscopic healing is defined as the complete absence of mucosal ulcerations in any ileocolonic segment.

Endoscopic Response (alternative definition)

The alternative definition of endoscopic response is >50% improvement from baseline in SES-CD or SES-CD score ≤ 2 .

Deep Remission

Deep remission is defined as achieving both clinical remission and endoscopic remission.

Deep Remission (Alternative Definition)

Deep remission (Alternative definition) is defined as achieving both clinical remission and endoscopic remission (Alternative definition).

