9.4.2. Primary Endpoints

The co-primary endpoints are:

- Clinical remission (CDAI score <150) at Week 12
- Endoscopic response (≥50% improvement from baseline in SES-CD score) at Week 12

Estimands and Estimators

Two co-primary estimands, ie, a precise definition of the primary targeted treatment effect, are defined by the following 5 attributes: treatment by Week 12, population, intercurrent events (ICEs) and corresponding strategies, variable (endpoint), and population-level summary.

Primary Estimand of Clinical Remission at Week 12

i. Treatment by Week 12:

Experimental: Combined guselkumab CCl induction dose group (ie, both guselkumab groups who received CCl at Weeks 0, 4, and 8; see Section 4.1)

Control: Placebo SC q4w (Weeks 0, 4, and 8)

ii. Population: Participants with moderately to severely active Crohn's disease

iii. Variable (endpoint):

A binary response variable (response/non-response) where response is defined as achieving CDAI score <150 at Week 12 without experiencing any of the ICEs in categories 1 to 3 as outlined below prior to the Week 12 visit.

iv. Intercurrent events and corresponding strategies:

The following are the ICEs considered for this study:

- 1) A Crohn's disease-related surgery (with the exception of minor procedures such as drainage of a superficial abscess or seton placement, etc.)
- 2) A prohibited change in Crohn's disease medication
- 3) Discontinuation of study intervention due to lack of efficacy or an AE of worsening Crohn's disease
- 4) Discontinuation of study intervention due to COVID-19 related reasons (excluding COVID-19 infection)
- 5) Discontinuation of study intervention due to COVID-19 infection, for reasons other than lack of efficacy or an AE of worsening Crohn's disease, or any other COVID-19 related reasons

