5.3. Co-Primary Endpoints Analysis

5.3.1. Definition of Endpoints

The co-primary endpoints are:

- Clinical remission at Week 12
- Endoscopic response at Week 12

Clinical remission is defined as a CDAI score <150.

Endoscopic response is defined as \geq 50% improvement from baseline in Simple Endoscopic Score for Crohn's Disease [SES-CD].

CDAI score

The CDAI is a validated multi-item measure of severity of illness derived as a weighted sum of 8 different Crohn's disease-related variables. These 8 variables are:

- extra-intestinal manifestations
- abdominal mass
- weight
- hematocrit
- use of antidiarrheal drug(s) and/or opiate
- total number of liquid or very soft stools
- abdominal pain/cramps
- general well-being.

Calculation of the CDAI score:

Two approaches to calculating the CDAI score are provided below. The main approach will be used for the analysis of all endpoints that include the CDAI; of particular note is that this main approach is used for the co-primary and secondary endpoints that involve the CDAI. Additional analyses of co-primary and secondary endpoints that involve the CDAI will also be provided using the alternative approach.

Main approach

The last 3 components of the CDAI score listed above are scored over 7 days by the participant on a diary card. For the total number of liquid or very soft stools, abdominal pain/cramps, and general well-being, if only 5 days or 6 days of data are available for the calculation, the weights of 7/5 and 7/6, respectively, will be used for the calculation; if the values are recorded for less than 5 days, the component will not be calculated.

The CDAI score calculation algorithm is presented in Section 10.8 Appendix 8 of the study protocol. At each timepoint, the CDAI score will only be calculated if \geq 4 of the 8 components are available. If the CDAI score cannot be calculated (ie, <4 components available), the CDAI score will be considered missing. When at least 4 of the 8 components are available, any missing components will be imputed by carrying forward the last non-missing value for that component.

Alternative approach

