The definitions of baseline disease activity and histologic remission using the GHAS System apply to a segment (region), Ileal, Colonic, and Subject level; the range of possible scores is 0 - 16 irrespective of extent of the area being analyzed. The binary (yes or no) endpoints histologic response, histo-endoscopic response, and histo-endoscopic remission will be evaluated on a subject level only.

Term	Scope	Definition
Baseline Active Disease (GHAS)	Subject-level	GHAS with a score > 0 for infiltration of
	Ileal Colonic	polymorphonuclear cells in the lamina propria, polymorphonuclear cells in epithelium, or presence of erosions and/or ulcers $[Q1 > 0 \text{ or } Q4 > 0 \text{ or } Q5 > 0 \text{ or } Q6 > 0]$
Histologic Response (GHAS)	Subject-level	\geq 50% reduction in subject-level GHAS score from baseline, or absence of mucosal neutrophils (epithelium and lamina propria), epithelial damage, erosions and ulceration [Q1 = 0, Q4 = 0, Q5 = 0 and Q6 = 0]

Histologic Remission (GHAS)	Subject-level Ileal Colonic	Absence of mucosal neutrophils (epithelium and lamina propria), epithelial damage, erosions and ulceration [Q1 = 0, Q4 = 0, Q5 = 0 and Q6 = 0]
Histo-Endoscopic Response (GHAS)	Subject-level	Combination of histologic response and endoscopic response (≥50% improvement from baseline in SES-CD score)
Histo-Endoscopic Remission (GHAS)	Subject-level	Combination of histologic remission and endoscopic remission (SES-CD \leq 4 and at least a 2-point reduction from baseline and no subscore greater than 1 in any individual component)
Histo-Endoscopic Remission (GHAS, Alternative Definition)	Subject-level	Combination of histologic remission and endoscopic remission (SES-CD Score <2).

Geboes Grading System

Histological disease activity will be scored in a blinded manner by an experienced pathologist using the Geboes Scoring system (GS). The GS is a 7-item scale (with 4 levels of severity for each item) that categorizes inflammation as grade 0 (architectural change only), grade 1 (chronic inflammation), grade 2 (2a, lamina propria eosinophils and 2b, lamina propria neutrophils), grade 3 (neutrophils in the epithelium), grade 4 (crypt destruction), or grade 5 (erosion or ulceration), as illustrated in Table 5.

Grade 0	Structural (architectural change)
Subgrades	
0.0	No abnormality
0.1	Mild abnormality
0.2	Mild or moderate diffuse or multifocal abnormalities
0.3	Severe diffuse or multifocal abnormalities
Grade 1	Chronic inflammatory infiltrate
Subgrades	

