Histologic Remission (GS)	Subject-level	\leq 2B.0 (i.e., no increase in neutrophils in lamina propria [GS
	Ileal	destruction [GS 4.0], and no erosions, ulcerations or
	Colonic	granulation tissue [GS 5.0])
Histo-Endoscopic	Subject-level	Histologic response and endoscopic response (≥50%
Response (GS)		improvement from baseline in SES-CD score)
Histo-Endoscopic Remission (GS)	Subject-level	Histologic remission and endoscopic remission (SES-CD ≤ 4 and at least a 2-point reduction from baseline and no subscore greater than 1 in any individual component)
Histo-Endoscopic Remission (GS, Alternative Definition)	Subject-level	Histologic remission and endoscopic remission (SES-CD Score ≤2).

Robarts Histologic Index

Histological disease activity will be scored by a blinded experienced pathologist using the Robarts Histopathology Index (RHI). The RHI is a 4-item index (with 4 levels for each item) that evaluates chronic inflammation, lamina propria neutrophils, neutrophils in the epithelium, and erosion or ulceration as illustrated in Table 6. Total score ranges from 0 to 33, where higher scores denote more severe inflammation.

Table 6: Robarts Histologic Index

Component

- 1. Chronic inflammatory infiltrate
- 0=No increase
- 1=Mild but unequivocal increase
- 2=Moderate increase
- 3=Marked increase

2. Lamina propria neutrophils

- 0=None
- 1=Mild but unequivocal increase
- 2=Moderate increase
- 3=Marked increase

3. Neutrophils in epithelium

0=None

1=<5% crypts involved

2=<50% crypts involved

3=>50% crypts involved

4. Erosion or ulceration

0=No erosion, ulceration or granulation tissue

1=Recovering epithelium+adjacent inflammation

1=Probable erosion—focally stripped

2=Unequivocal erosion

3=Ulcer or granulation tissue

RHI = 1 x chronic inflammatory infiltrate level (4 levels)

+ 2 x lamina propria neutrophils (4 levels)

+ 3 x neutrophils in epithelium (4 levels)

+ 5 x erosion or ulceration (4 levels)

That is, RHI incorporates four components from the Geboes score (Grades 1, 2B, 3, and 5) into a weighted sum of the subgrades using the following formula,

RHI = 1*GS1 + 2*GS2B + 3*GS3 + 5*GS5

All components need to be scored with the re-parameterized grade score (Grade 5) to calculate the RHI.

If any of the components needed to calculate the RHI is missing, then the RHI will be set to missing.

All components need to be scored with the re-parameterized grade score (Grade 5) to calculate the RHI.

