- At each time point, all biopsies (up to 2 biopsies per region) obtained from each of the predefined anatomic regions will be scored separately for each of the 4 items:
- The single highest scoring item from each of the biopsies will be used as the score for that item.
- The weighted sum of the 4 scores within a region will be used as the Total score for that region (range 0-33). Furthermore,
 - The Ileal score will be equal to the Total Ileum Score
 - The worst scores for each item across the right colon, transverse colon, left colon, and rectum will be summed to obtain a Total Colonic Score.
 - The worst scores for each item across the 5 regions will be summed to obtain a Subject Score.

If both biopsies within a region are missing or unevaluable, the RHI will be missing for that region.

The definitions of baseline disease activity and histologic remission using RHI apply to a segment (region), Ileum, Colon, and Subject level. Histologic response, histo-endoscopic response, and histo-endoscopic remission will be evaluated on a subject level only.

Term	Scope	Definition			
Active Disease (RHI)	Subject-level	RHI with a score > 0 for any of Items 2-4 of RHI (lamina propria			
	Ileal	neutrophils, neutrophils in epithelium, or erosions or ulcerations)			
	Colonic				
Histologic Response (RHI)	Subject-level	\geq 50% reduction in RHI score from baseline or sub-scores of lamina propria neutrophils and neutrophils must be equal to 0, with no ulcers or erosions			
Histologic Remission	Subject-level	sub-scores of lamina propria neutrophils, neutrophils in the			
(RHI)	Ileal	epithelium and erosions or ulcerations must be equal to 0.			
	Colonic				
Histo-Endoscopic Response (RHI)	Subject-level	Histologic response and endoscopic response (≥50% improvement from baseline in SES-CD score)			
Histo-Endoscopic Remission (RHI)	Subject-level	Histologic remission and endoscopic remission (SES-CD ≤4 and at least a 2-point reduction from baseline and no subscore greater than 1 in any individual component)			
Histo-Endoscopic	Subject-level	Histologic remission and endoscopic remission (SES-CD Score			
Remission (RHI		≤2).			
Alternative Definition)					

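### GHAS alternative histo-endoscopic remission uses SES-CD <2 where the rest of the SAP uses ≤2; the alternative endoscopic response is only the main definition without exact halvings

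*SAP*

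**What the plan says.** **Endoscopic remission, alternative definition.** SAP 5.5.1.2 sets a single cut-point: "definition of endoscopic remission is an SES-CD Score ≤ 2". The alternative histo-endoscopic remission endpoints in SAP 5.5.1.5 combine histologic remission with that remission, but restate the cut-point in each table:

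- GHAS: "Combination of histologic remission and endoscopic remission (SES-CD Score <2"
- Geboes: "Histologic remission and endoscopic remission (SES-CD Score ≤2"
- RHI: the same wording as Geboes, with ≤2

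SAP 5.5.2.10 lists all three for Weeks 12, 48 and 96.

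**Endoscopic response.** The co-primary definition in Protocol 9.4.2 is "Endoscopic response (≥50% improvement from baseline in SES-CD score) at Week 12". SAP 5.3.1 and all three histo-endoscopic response definitions in SAP 5.5.1.5 use the same ≥50%. SAP 5.5.1.2 adds: "The alternative definition of endoscopic response is >50% improvement from baseline in SES-CD", or a score of 2 or less. SAP 5.5.2.5 lists this alternative for Weeks 12, 48 and 96. Neither document says what it is meant to capture.

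**The concern.** The GHAS row is an internal conflict. One endpoint name has two endoscopic components, and nothing in the SAP explains why. A programmer who reuses the remission variable from 5.5.1.2 codes ≤2, and one who follows the GHAS row codes <2. Both can claim to follow the plan, and their results differ for everyone with a score of exactly 2.

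The alternative response raises a question of purpose. It adds a low-score route (≤2) but moves the percentage rule from ≥50% to >50%. The total SES-CD is a sum of whole-number cells, so a fall of exactly one half can occur. It is worth asking whom the alternative classifies differently from the main definition, and whether that was intended.

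**Working it through.** **Plan's own figure.** The only stated number that rests on an endoscopic response definition is the power for the co-primary: 94% for 13% versus 30%, with 106 and 212 participants and a two-sided chi-square test at 0.05 (Protocol 9.2, Table 8).

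- Pooled rate: (106×0.13 + 212×0.30)/318 = 77.38/318 = 0.2433
- Standard error under no difference: √[0.2433×0.7567×(1/106 + 1/212)] = 0.0510
- Standard error under the alternative: √[0.13×0.87/106 + 0.30×0.70/212] = 0.0454
- Power: Φ[(0.17 − 1.96×0.0510)/0.0454] = Φ(1.54) = 0.9385

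This agrees with the stated 94%. It uses the main ≥50% rule, so nothing below alters it.

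**Remission cut-points.** For a whole-number score *y*:

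| Place in SAP | Endpoint | Rule | *y* = 1 | *y* = 2 | *y* = 3 |
|---|---|---|---|---|---|
| 5.5.1.2 | Alternative endoscopic remission | ≤2 | yes | yes | no |
| 5.5.1.5 | Alternative histo-endoscopic remission, Geboes | ≤2 | yes | yes | no |
| 5.5.1.5 | Alternative histo-endoscopic remission, RHI | ≤2 | yes | yes | no |
| 5.5.1.5 | Alternative histo-endoscopic remission, GHAS | <2 | yes | **no** | no |

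The rules differ at one value only, *y* = 2.

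**Response definitions.** Let *b* be baseline and *y* the later score.

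- Inputs: entry requires a score of at least 6, or at least 4 for isolated ileal disease (Protocol 5.1; SAP 1.2), so *b* ≥ 4. The total runs from 0 to 56 (SAP 5.3.1).
- Main: 100×(*b* − *y*)/*b* ≥ 50, which is *y* ≤ *b*/2.
- Alternative as printed: *y* < *b*/2, or *y* ≤ 2.

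Step 1. If *b* ≥ 4 then *b*/2 ≥ 2, so any *y* ≤ 2 already satisfies *y* ≤ *b*/2. The low-score arm adds nobody beyond the main definition.

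Step 2. A main responder fails the alternative only if *y* = *b*/2 and *y* > 2, that is, *b* even and at least 6. These pairs are 6→3, 8→4, 10→5, and so on to 56→28: (56 − 6)/2 + 1 = 26 pairs. The pair 4→2 passes both definitions, and is the only pair that the low-score arm rescues from the strict sign.

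Step 3. Listing all 53×57 = 3,021 combinations of *b* (4 to 56) and *y* (0 to 56) gives 26 that meet the main definition and fail the alternative, and 0 that do the reverse.

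Step 4. With ≥50% in the alternative, the rule becomes *y* ≤ *b*/2 or *y* ≤ 2. By Step 1 this is the main definition, with 0 discordant combinations.

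**Size.** At full enrolment, each participant whose status changes moves the rate by 1/106 = 0.94 percentage points in a single arm, or 1/212 = 0.47 points in the combined guselkumab group. The documents give no count at an exact halving or at a score of 2. As an assumption only, 1% to 5% of 318 would be about 3 to 16 participants. For the GHAS endpoint, only those who also reach histologic remission would change status.

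**The case against.** Four points can be made on the other side.

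*The signs may be misread.* Inequality signs are not steady in the text as read from the PDF. Protocol 9.4.3 prints the strata as ≤300 or ≥300 and ≤12 or ≥12, where 9.4.2 prints >300 and >12. SAP 5.5.2.5 prints a fecal calprotectin cut of ≥250 where 5.5.2.7 prints >250. This stands as a reason to check the source before editing. It does not settle the matter: those differences run the other way (an equality bar appears rather than disappears), the sentence with >50% shows ≤2 correctly, and the GHAS table shows ≥50% and ≤4 correctly in the rows above <2. If the source shows ≤2 for GHAS, that half of the point falls. If it shows ≥50% for the alternative response, the redundancy remains.

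*An alternative may differ from the main definition.* This is right. A reader might call >50% against ≥50% a contradiction, but ≥50% is the main rule, it is used consistently, and the other rule is labelled as an alternative. What is missing is a reason for it.

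*The three histologic indices differ by design.* This also stands. A reader might infer that the three alternative histo-endoscopic rates cannot be compared because of the cut-point, or that GHAS must come out lowest. The documents do not support either. Geboes and RHI share ≤2. The histologic parts differ too: GHAS requires no epithelial damage, Geboes no crypt destruction, and RHI neither. No comparison of the three is planned. All that follows is that GHAS with <2 cannot exceed GHAS with ≤2.

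*The endpoints are exploratory.* SAP 5.5 and 5.5.3 give them nominal p-values, so no controlled conclusion depends on them.

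**Conclusion.** The point holds as a minor one, in two parts.

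The GHAS row conflicts with the SAP's own alternative remission and with the two parallel endpoints. The conflict affects exactly one score value, at three visits.

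The alternative endoscopic response is strictly narrower than the main definition for every eligible baseline, and differs only by excluding exact halvings from even baselines of 6 or more. A reader might take the added ≤2 route as a sign that the alternative is meant to be broader, or that it loosens one part while tightening another. Neither document states such an intent, and the entry minimum makes a broader result impossible. The route could add responders only at baselines below 4, which the entry criteria exclude and for which waivers are not allowed.

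The conclusion rests on whole-number totals, on baselines of at least 4, and on the inequality signs being as printed. Any estimate of the effect on a rate would need a distribution of SES-CD scores that the documents do not give. The co-primary endpoint, the controlled Week 48 endoscopic response and the power are unaffected.

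**What to change.** 1. Check the GHAS row against the source document. If it prints <2, change it to ≤2, or replace all three restated cut-points with a reference to the alternative endoscopic remission in 5.5.1.2. If tables have already been produced, record which cut-point was programmed.
2. For the alternative endoscopic response, confirm the sign and add one sentence on its purpose. If ≥50% was intended, delete the definition in 5.5.1.2 and its line in 5.5.2.5, because it duplicates the main endpoint. Changing the sign alone would leave a redundant endpoint. If >50% was intended, say that it excludes exact halvings and that the ≤2 route then matters only for a fall from 4 to 2.

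The cost is one symbol for the first item, and one sentence or two deletions for the second. No data collection, sample size or testing order changes.

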5.5.1.3. Fistula

Fistula Response

Fistula Response is defined as $\geq 50\%$ reduction from baseline in number of open or draining fistulas, among participants with 1 or more fistulas at baseline.

Complete Fistula Response

Complete Fistula Response is defined as 0 open or draining fistulas, among participants with 1 or more fistulas at baseline.

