5.2. Exclusion Criteria

Any potential participant who meets any of the following criteria will be excluded from participating in the study:

- 1. Has complications of Crohn's disease, such as symptomatic strictures or stenoses, short gut syndrome, or any other manifestation, that might be anticipated to require surgery, could preclude the use of the CDAI to assess response to therapy, or would possibly confound the ability to assess the effect of treatment with guselkumab.
- 2. Currently has or is suspected to have an abscess. Recent cutaneous and perianal abscesses are not exclusionary if drained and adequately treated at least 3 weeks before baseline, or 8 weeks before baseline for intra-abdominal abscesses, provided that there is no anticipated need for any further surgery. Participants with active fistulas may be included if there is no anticipation of a need for surgery and no abscesses are currently identified.
- 3. Has had any kind of bowel resection within 24 weeks, or any other intra-abdominal or other major surgery within 12 weeks, before first dose of study intervention.
- 4. Has a draining (ie, functioning) stoma or ostomy.
- 5. Presence on screening endoscopy of adenomatous colonic polyps, if not removed before study entry, or history of adenomatous colonic polyps that were not removed.
- 6. Has a stool culture or other examination positive for an enteric pathogen, including *Clostridioides difficile* (formerly known as *Clostridium difficile*) toxin, within 4 months before the first dose of study intervention, unless a repeat examination is negative and there are no signs of ongoing infection with that pathogen.

Note: Treatment and repeat testing can occur in the current screening period.

Concomitant or Previous Medical Therapies Received

- 7. Has received any of the following prescribed medications or therapies within the specified period:
 - a. IV corticosteroids received within 3 weeks of baseline
 - b. Cyclosporine, tacrolimus, sirolimus, or mycophenolate mofetil received within 8 weeks of baseline
 - c. 6-thioguanine received within 4 weeks of baseline
 - d. Biologic agents:
 - 1) Anti-TNFα therapy (eg, infliximab, etanercept, certolizumab pegol, adalimumab, golimumab) received within 8 weeks of baseline
 - 2) Vedolizumab received within 12 weeks of baseline

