C-reactive protein has been demonstrated to be useful as a marker of inflammation in patients with IBD. In Crohn's disease, elevated CRP concentrations have been associated with severe clinical activity, elevated sedimentation rate, and active disease as detected by colonoscopy (Solem 2005). Blood samples for the measurement of CRP will be collected from all participants at the time points specified in the SoA (Section 1.3). CRP will be evaluated using a validated, high-sensitivity assay.

Fecal calprotectin has been demonstrated to be a sensitive and specific marker in identifying intestinal inflammation and response to treatment in patients with IBD (Costa 2005). Stool samples for fecal calprotectin concentration will be collected from all participants at the time points

specified in the SoA (Section 1.3) through on-site or at-home collection. The assay for fecal calprotectin concentration will be performed using a validated method.

Fistula assessment will be performed in all participants on an ongoing basis throughout the duration of the study through physical examination. All participants will be assessed for fistulas at baseline. For participants with fistulizing disease, fistula closure will be assessed during the study. Enterocutaneous fistulas (eg, perianal and abdominal) will be considered no longer draining (ie, closed) when there is absence of drainage despite gentle compression. Rectovaginal fistulas will be considered closed based on either physical examination or absence of relevant symptoms (eg, passage of rectal material or flatus from the vagina).

Patient-reported outcome measures will be evaluated at visits as indicated in the SoA (Section 1.3):

- The **IBDQ** is a validated, 32-item, self-reported questionnaire for participants with IBD to assess disease-specific HRQOL by evaluating PROs across 4 dimensions: bowel symptoms (loose stools, AP), systemic symptoms (fatigue, altered sleep pattern), social function (work attendance, need to cancel social events), and emotional function (anger, depression, irritability) (Irvine 1994). Scores range from 32 to 224, with higher scores indicating better outcomes. Participants will complete the IBDQ on site.

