5.5.2.4. Abdominal Pain and Stool Frequency

- AP score (daily average based on the CDAI assessment) ≤1 over time, among participants with daily average AP score >1 at baseline
- Number of liquid or very soft stools (daily average based on the CDAI assessment) ≤ 3 over time, among participants with daily average number of liquid or very soft stools >3 at baseline
- Absence and/or resolution of abdominal pain (defined as a mean daily CDAI AP score of 0 in the week prior to the visit) among participants with mean AP>1 at baseline, over time
- SF remission (defined as number of liquid or very soft stools daily average based on CDAI assessment SF ≤ 1.5 in the week prior to the visit) among participants with mean SF >2.5 at baseline, over time

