5.5.2.6. Fistula

- Fistula response over time, defined as a ≥50% reduction from baseline in the number of draining fistulas, among participants with 1 or more fistulas at baseline
- Complete fistula response over time, among participants with 1 or more fistulas at baseline

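### The fistula endpoints count open or draining fistulas but are analysed in everyone with any fistula at baseline, so on a literal reading a participant with nothing to close can be a complete responder

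*SAP*

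**What the plan says.** SAP 5.5.1.3 defines two endpoints. Fistula response is a 50% or greater "reduction from baseline in number of open or draining fistulas, among participants with 1 or more fistulas at baseline". The second definition reads: "Complete Fistula Response is defined as 0 open or draining fistulas, among participants with 1 or more fistulas at baseline".

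The endpoint list in SAP 5.5.2.6 repeats the unqualified denominator for the second endpoint: "Complete fistula response over time, among participants with 1 or more fistulas at baseline". For the first it counts differently, as a 50% or greater "reduction from baseline in the number of draining fistulas, among participants with 1 or more fistulas at baseline". Fistulas that are open or draining have become fistulas that are draining.

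Protocol 8.1 says "All participants will be assessed for fistulas at baseline", by physical examination, with closure then followed in participants with fistulizing disease. Of enterocutaneous fistulas it says that they "will be considered no longer draining (ie, closed) when there is absence of drainage despite gentle compression". Exclusion criterion 2 in Protocol 5.2 permits active fistulas without requiring them: "Participants with active fistulas may be included if there is no anticipation of a need for surgery and no abscesses are currently identified".

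**The concern.** An endpoint meant to show closure should be measured in participants who have something to close. Here the numerator is restricted by status and the denominator is not. A participant with only non-draining fistulas at baseline can be eligible, has a fistula, and has a count of zero for the quantity that the endpoint requires to be zero.

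Two things follow. The complete-response rate in each arm would partly describe fistulas that were closed from the start. The two endpoints would also lose their natural nesting, because such a participant can be a complete responder with no defined fistula response.

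The SAP handles comparable endpoints differently. In 5.5.2.4 it specifies "AP score (daily average based on the CDAI assessment) ≤1 over time, among participants with daily average AP score >1 at baseline", and it restricts stool frequency in the same way. In 5.5.2.7 the CRP and fecal calprotectin thresholds are restricted to participants with elevated values at baseline. In 5.5.2.9 the pain-scale reduction requires a baseline score of at least 3, and in 5.5.2.10 histologic remission requires histologic disease at baseline. The fistula endpoints depart from that convention, which suggests an omission and not a deliberate choice.

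**Working it through.** The documents give no rate, count, sample size or power for the fistula endpoints, so there is no figure of the plan's to reproduce. The check applies the definitions to cases and then shows what the effect on a treatment difference depends on.

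**Step 1: apply the definitions.** Let b be the number of open or draining fistulas at baseline and p the number at a later visit. From SAP 5.5.1.3:

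- in the denominator if there is at least one fistula of any status at baseline;
- complete response if p = 0;
- fistula response if (b - p)/b ≥ 0.5.

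| Fistulas at baseline, any status | b | p | Complete-response criterion at baseline | Complete response at visit | Fistula response at visit |
|---|---|---|---|---|---|
| 1 | 0 | 0 | met | met | 0/0, undefined |
| 2 | 0 | 1 | met | not met | -1/0, undefined |
| 2 | 1 | 0 | not met | met | 1/1 = 100%, met |
| 2 | 2 | 1 | not met | not met | 1/2 = 50%, met |
| 2 | 2 | 0 | not met | met | 2/2 = 100%, met |

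All five participants are in the denominator. The criterion is already met at baseline, and fistula response is undefined, exactly when b = 0.

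**Step 2: what a programmer would do with b = 0, p = 0.** Coded as (b - p)/b ≥ 0.5, the result is missing, and non-responder imputation (SAP 5.4.3.1, applied to exploratory binary endpoints by 5.5.3) may turn it into non-response. Coded as p ≤ 0.5b, the test is 0 ≤ 0 and gives response. The SAP has no rule to choose between them.

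**Step 3: effect on the treatment difference.** Let f be the share of the denominator with b = 0, r the closure rate among the rest, and s the proportion of the b = 0 participants who count as complete responders at the visit (retention). In each arm

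observed rate = f·s + (1 - f)·r,

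so, with f equal in the arms,

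observed difference = (1 - f)(r_gus - r_pbo) + f(s_gus - s_pbo).

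All values below are assumed for illustration; none is in the documents. Take r = 40% on guselkumab and 20% on placebo, a difference of 20 points.

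- f = 10%, s = 100% in both arms: 0.10 + 0.90 × 0.40 = 46% and 0.10 + 0.90 × 0.20 = 28%; difference 18 points.
- f = 30%, s = 100% in both arms: 0.30 + 0.70 × 0.40 = 58% and 0.30 + 0.70 × 0.20 = 44%; difference 14 points.
- f = 30%, s = 95% on guselkumab and 70% on placebo: 0.285 + 0.28 = 56.5% and 0.21 + 0.14 = 35%; difference 21.5 points.

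The first two show shrinkage by (1 - f). The third shows none, because f(s_gus - s_pbo) = 0.30 × 25 = 7.5 points offsets the loss of 6.

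**Step 4: after the change.** If the denominator requires b ≥ 1, nobody meets complete response at baseline, (b - p)/b is always defined, and p = 0 gives (b - 0)/b = 100%, so every complete responder is a responder.

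**The case against.** The strongest reply is that the documents never say that a closed tract counts as a fistula at baseline. The counting unit in 5.5.1.3 is the open or draining fistula, and Protocol 8.1 speaks of assessing closure, which presupposes something open. If the case report form records only open or draining fistulas at baseline, the denominator is already right. This stands as a condition on the point. It does not remove it, because neither document states the restriction and Protocol 8.1 gives closed as a possible status.

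A reader might infer that these participants are scored as complete responders on Day 1. They are not. The endpoint is assessed over time, and the intercurrent-event rules of SAP 5.4.2.1 and non-responder imputation apply to it. Surgery, prohibited medication changes, most discontinuations and meeting the rescue criteria all give non-response, as do missing data. What holds is that the criterion is met at baseline without any change.

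A reader might also infer that the treatment difference is necessarily diluted. Step 3 shows that this needs equal retention across arms. Meeting the rescue criteria is a composite event, and if the drug works it would be expected more often on placebo, so equal retention cannot be taken for granted once rescue has been assessed at Weeks 12 and 16.

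Internal fistulas are a tempting further example, but the documents do not support it. Assessment is by physical examination, so a fistula that examination cannot detect would not enter the denominator by that route.

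The difference between counting open or draining fistulas and counting draining ones is small, since Protocol 8.1 equates no longer draining with closed for enterocutaneous fistulas. It is still two wordings for one endpoint.

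**Conclusion.** The point holds on the text. The denominator in SAP 5.5.1.3 and 5.5.2.6 admits participants with no open or draining fistula at baseline. For them the complete-response criterion is met from the start and fistula response is undefined, so the two endpoints are not nested.

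This rests on one assumption: that non-draining fistulas can be recorded as fistulas at baseline.

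The size is unknown. The documents give neither f nor the number of participants with fistulas, so calling the loss material would go beyond them. The shrinkage by (1 - f) is conditional on equal retention.

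The consequence is limited. The fistula endpoints are exploratory, lie outside the multiplicity procedure and carry nominal p-values. A reader might infer some effect on the trial's main conclusions, but no co-primary, secondary or multiplicity-controlled Week 48 result depends on them. The correction is still worth making, because it repairs a stated rule, follows the SAP's own convention and costs little.

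**What to change.** In SAP 5.5.1.3 and 5.5.2.6, define both fistula endpoints for participants who have at least one open or draining fistula at baseline. Use the open-or-draining count in both sections, for the baseline and the post-baseline value; 5.5.2.6 now counts draining fistulas only. If the case report form already records only open or draining fistulas at baseline, the same sentence documents that fact.

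The cost is SAP wording. No new data collection is needed, because the Schedule of Activities already places fistula assessment at Week 0 and at on-site visits through Week 96. The downside is a slightly smaller denominator, limited to participants in whom closure can be shown.
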